**PARTNERS HUMAN RESEARCH COMMITTEE
PROTOCOL SUMMARY**

Answer all questions accurately and completely in order to provide the PHRC with the relevant information to assess the risk-benefit ratio for the study. Do not leave sections blank.

PRINCIPAL/OVERALL INVESTIGATOR

[name]

PROTOCOL TITLE

An Open-Label Clinical Trial Conducted via Telepsychiatry of Complementary and Alternative Treatments (Omega-3 Fatty Acids and Inositol vs. N-acetylcysteine) for the Management of Emotional Dysregulation in Youth with Non-verbal Learning Disability (NVLD) and/or Autism Spectrum Disorders (ASD)

FUNDING

Sponsored by Demarest Lloyd, Jr. Foundation

VERSION DATE

Version: AME 29

Last Modified Date: 2/22/2023

SPECIFIC AIMS

Concisely state the objectives of the study and the hypothesis being tested.

The purpose of this study is to examine the relative effectiveness of omega-3 fatty acids plus inositol versus N-acetylcysteine (NAC) in reducing symptoms of emotional dysregulation in children and adolescents (ages 5-17) with non-verbal learning disability (NVLD) and/or autism spectrum disorders (ASD). We hypothesize that omega-3 fatty acids plus inositol combined intervention will result in improved outcomes relative to using NAC as monotherapy.

BACKGROUND AND SIGNIFICANCE

Provide a brief paragraph summarizing prior experience important for understanding the proposed study and procedures.

Emotional dysregulation affects a sizeable minority of children with non-verbal learning disability (NVLD) and related conditions such as autism spectrum disorders (ASD). The occurrence of a mood disorder in these children and adolescents further compromises their problematic course and outcome. Unfortunately, none of the current conventional treatments for mood disorders can claim a high level of efficacy combined with easy tolerability in all individuals. Increasingly, clinicians, researchers, and patients and their families are turning to natural products considered

complementary and alternative treatments. Yet, few studies exist to support the use of these dietary supplements in pediatric populations.

Omega-3 fatty acids (including EPA and DHA) are important components of cell membranes and are important for cell-to-cell communication in the brain. However, abnormalities in fatty acid composition of phospholipids in cell membranes have been described in psychiatric disorders in general and in bipolar disorder in particular (Horrobin & Bennett, 1999; Horrobin, Glen, & Vaddadi, 1994; Peet, Murphy, Shay, & Horrobin, 1998; Stoll et al., 1999). With reduced omega-3 fatty acids, the fatty acid composition of the cell membrane phospholipids would be altered, possibly leading to altered neurotransmitter binding and psychopathology. Thus, supplementing omega-3 fatty acids is suggested to have a potentially therapeutic role in the management of mood disorders.

Inositol is a precursor for, as well as a product of, the phosphatidylinositol (PI) cycle and is therefore common and widely found, located primarily within cell membranes (Baraban, Worley, & Snyder, 1989). Although the mechanism of action of inositol remains unclear, we can indirectly presume from the available evidence that subjects with mood disorders experience a decrease in brain myo-inositol, which adversely affects the functioning of the PI second messenger system, which in turn results in mood changes. Dietary supplement with inositol, therefore, could improve the functioning of the PI system and treat depressive symptoms.

N-acetylcysteine (NAC) is an acetylated amino acid and a precursor of glutathione that acts as an antioxidant in the brain to reduce oxidative stress, which has been implicated in bipolar disorder and major depression (Magalhaes et al., 2011). The main interest in psychiatry involves NAC as a precursor to glutathione, which acts as a potent antioxidant diminishing free radicals that can lead to cell damage and death. Glutathione is a major endogenous antioxidant in the brain. Glutathione is a molecule comprising three peptides: glutamate, cysteine, and glycine. The addition of the cysteine is the rate-limiting step, and NAC provides this key substrate for the creation of glutathione.

Recent work by our group has shown improvements in emotional dysregulation in youth using omega-3 fatty acids (Wilens et al., 2017; Wozniak et al., 2007) and an even more robust outcome when combining omega-3 fatty acids with inositol (Wozniak et al., 2015; Wozniak et al., 2016). Work by our group also suggests that N-acetylcysteine (NAC) is helpful in the management of emotional dysregulation in youth. However, these studies are not directly comparable as they were conducted at different times with different study clinicians and age groups.

Additionally, a major limitation of the previous clinical trials by our group on the efficacy of natural supplements is the burden on families incurred by travel to appointments. In our previous clinical trials, recruitment, retention, and patient satisfaction were all negatively impacted by the need to come into the office for study visits. Telepsychiatry is an established and rapidly growing initiative in the Department of Psychiatry at MGH. [name] has lead the department in using virtual visits to connect with patients and provide clinical psychiatric care. She has personally championed the use of virtual visits with the autism spectrum population, for whom the adverse sensory experience of a hospital visit is especially burdensome.

Since omega-3 fatty acids, inositol, and NAC are safe with nor serious associated adverse events, studies of these treatments are well suited to virtual visits. Our preliminary data with all three supplements demonstrated minimal adverse events and no medical safety events. Therefore, this study is proposed to examine the relative effectiveness of omega-3 fatty acids and inositol versus NAC using telemedicine to conduct study visits. This will allow for a comparison of these natural supplements for the treatment of emotional dysregulation while providing subjects and their families with a more convenient and pleasant experience, which will most likely positively impact both recruitment and subject satisfaction and retention.

RESEARCH DESIGN AND METHODS

Briefly describe study design and anticipated enrollment, i.e., number of subjects to be enrolled by researchers study-wide and by Partners researchers. Provide a brief summary of the eligibility criteria (for example, age range, gender, medical condition). Include any local site restrictions, for example, "Enrollment at Partners will be limited to adults although the sponsor's protocol is open to both children and adults."

This will be a 6-week, open-label, randomized clinical trial study to compare efficacy and tolerability of the natural treatments omega-3 fatty acids, inositol, and NAC in the treatment of mood dysregulation in children and adolescents with NVLD/ASD. Subjects will include youth ages 5-17 years with a non-verbal learning disability (NVLD) or autism spectrum disorder (ASD) and current symptoms of emotional dysregulation. We will enroll 60 subjects to allow for the randomization of 30 subject into each treatment arm.

The full inclusion and exclusion criteria are included below:

A. Inclusion Criteria:

1. Male or female subjects, 5-17 years of age.
2. A previous established diagnosis of non-verbal learning disability (NVLD) or DSM-V Autism Spectrum Disorder and/ or combined T-scores on the Child Behavior Checklist \geq 195 on the Withdrawn + Social Problems + Thought Problems subscales.

3. Current symptoms of emotional dysregulation as indicated by combined T-scores on the Child Behavior Checklist ≥ 180 on the Anxiety/Depression + Aggression + Attention subscales.
4. Subjects and their caregivers must be English-speaking and have a level of understanding sufficient to communicate intelligently with the investigator and study coordinator, and to cooperate with all tests and examinations required by the protocol.
5. Subjects and their caregivers must be willing and able to comply with all study procedures.
6. Each subject and his/her authorized legal representative must understand the nature of the study. The subject's authorized legal representative must sign an informed consent document and the subject must sign an informed assent document.
7. Subject must be able to swallow pills.
8. Subject must have access to a computer with a camera, speaker, microphone, and internet connection.
9. Subjects must be willing to refrain from treatment changes during the study protocol.

B. Exclusion Criteria:

1. Investigator and his/her immediate family; defined as the investigator's spouse, parent, child, grandparent, or grandchild.
2. Serious or unstable illness including hepatic, renal, gastroenterological, respiratory, cardiovascular (including ischemic heart disease), endocrinologic, neurologic, immunologic, or hematologic disease.
3. History of bleeding diathesis, including those with von Willebrand disease.
4. Uncorrected hypothyroidism or hyperthyroidism.
5. History of sensitivity to omega-3 fatty acids, inositol or NAC. A non-responder or history of intolerance to omega-3 fatty acid, inositol or NAC after 2 months of treatment at adequate doses as determined by the clinician.
6. Severe allergies or multiple adverse drug reactions.
7. Unstable or untreated seizure disorder.
8. DSM-IV substance use, abuse or dependence.
9. Judged clinically to be at serious suicidal risk for C-SSRS score ≥ 4 .
10. Current diagnosis of schizophrenia.
11. Current diagnosis or symptoms of psychosis.
12. IQ < 70.
13. Pregnant or nursing.
14. Weighs less than 12.5kg.

The main outcome measures will be improvement in manic symptoms as measured by the Parent-Young Mania Rating Scale (P-YMRS) and improvement in depressive symptoms as measured by the parent-completed Children's Depression Inventory (CDI) scale.

Only subjects who are not responding to their current treatment regimen will be recommended to taper from their medications. No subject on a useful treatment will be recommended to taper from medication for entry into this study. Subjects and their current treating prescriber may opt to continue with current treatment even if taper is recommended. Typically, a 7-day washout period is recommended for antidepressant medications and atomoxetine (with the exception of Prozac requiring 14 days). Mood stabilizers/atypical antipsychotics are generally washed out over the course of 7 days, while stimulants are discontinued in 3 days. Discontinuation of medications will be done in consultation with the prescribing clinician.

We plan to treat subjects with the following doses:

Omega-3 Fatty Acids

All subjects: 1020mg QAM + 1020mg QPM

+

Inositol

Subjects under 25kg: 1000mg daily

Subjects weighing 25kg or more: 2000mg daily

OR

NAC:

Effervescent Tablets

Subjects ages 5-12: 1800mg daily

Subjects ages 13-17: 2700 mg daily

Capsules

Subjects ages 5-12: 1800mg daily

Subjects ages 13-17: 2400mg daily

At each visit, measures of safety and effectiveness will be obtained using rating scales.

Briefly describe study procedures. Include any local site restrictions, for example, "Subjects enrolled at Partners will not participate in the pharmacokinetic portion of the study." Describe study endpoints.

Interested parents/guardians will first complete a phone screen with the study coordinator or a research assistant. If the child meets eligibility criteria based on the phone screen, the parent/guardian will be asked to complete the Child Behavior Checklist (CBCL) via RedCap, a secure online data capture system. The parent/guardian will be provided with an online consent statement and asked to indicate their agreements to participate in the online questionnaire portion of the study before they are brought the CBCL.

If a parent/guardian has completed pre-screening procedures for another research study or the clinic in our department within the past 3 months, they will not be asked to complete that procedure again, and the data collected previously will be used for pre-screening for this protocol.

Subjects deemed to be eligible following the phone screen and completion of the CBCL will either be scheduled for an in-person visit at our office or, during the COVID-19 pandemic, to speak with a study clinician via phone to obtain informed consent prior to completing further screening and baseline study procedures via virtual visit. Informed consent will be obtained from all subjects and their legal guardian at the initial in-person visit or, during the COVID-19 pandemic, during a phone call with a study clinician. The subject's legal guardian will then answer questionnaires regarding current medications and demographic details. They will also complete the BRIEF, SRS, P-YMRS, and CDI questionnaires. A study clinician will complete the Columbia Suicide Severity Rating Scale (C-SSRS) to assess past and current suicidality and self-harmful behaviors; conduct an observational mental status exam; record baseline severity scores of Clinical Global Impression (CGI) for mania, depression, and overall bipolar disorder; and will review current medications and recommend any medication taper. A trained member of study staff will obtain and record height and weight for all subjects. A urine pregnancy test will be conducted for all female subjects who have reached menstruation. If the test is positive, the subject will not be able to participate in the study and she will be informed of the results, along with her parent/guardian if she agrees. Even if she does not agree, the study doctor may still decide, based on the subject's age, maturity, or medical condition, to inform the parent/guardian.

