Natural Treatments for the Management of Emotional Dysregulation in Youth With Non-verbal Learning Disability (NVLD) and/or Autism Spectrum Disorders (ASD)

NCT03757585

April 23, 2025

Statistical Methods

Participants were included in the analysis based on a modified intent to treat analysis plan with the criterion that participants had to be exposed to the study medications for ?2 weeks. Baseline clinical characteristics were examined using Pearson's chi-squared test for dichotomous measures and truncated Poisson regression models for continuous measures (CBCL-AAA and CBCL-AT: lower level [II] of truncation=150, upper level [ul] of truncation=270; SRS: ll=30, ul=90; BRIEF: ll=30, ul=100; YMRS: ul=60; CDI: ul=40). Primary efficacy measures of mania and depression, as well as secondary measures of autism symptoms and executive functioning, were analyzed using mixed-effects Poisson regression models predict the outcome measure of interest from the study group, study week (continuous), and the study group-by-study week interaction, which is the primary effect of interest. Secondary efficacy measures of mania and depression assessed at endpoint were examined using logistic regression models predicting the outcome of interest from the study group. Adverse events (AEs) were analyzed using a Poisson regression model for AE counts and Fisher's exact tests for AE prevalence. All analyses were two-tailed with an alpha level of 0.05 and conducted using Stata (Version 18.1) (StataCorp, 2023).

We also examined the moderating effect of 1) the CBCL Autistic Traits (AT) profile defined by a combined T-score ?195 on the CBCL Withdrawn/Depressed, Social Problems, and Thought Problems scales, and 2) the CBCL-Bipolar (BP) profile defined by a combined T-score ?210 on the CBCL Aggressive Behavior, Attention Problems, and Anxious/Depressed scales. To examine these moderating effects, we added a 3-way interaction term between study group, study visit, and CBCL profile group to each of the models for the primary and secondary outcomes of interest. The moderating effects of the CBCL-AT and CBCL-BP profiles were examined separately.

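### The efficacy models make no adjustment for psychotropic treatment at entry, which the protocol lets children continue: the comparison stays valid, but modest precision is lost and chance imbalance goes uncorrected

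*Protocol*

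**What the plan says.** **Background treatment.** Under Research Design and Methods, the protocol limits taper advice to non-responders: "Only subjects who are not responding to their current treatment regimen will be recommended to taper from their medications". It adds: "No subject on a useful treatment will be recommended to taper from medication for entry into this study". Advice to taper may also be declined: "Subjects and their current treating prescriber may opt to continue with current treatment even if taper is recommended". The classes discussed are antidepressants, atomoxetine, mood stabilisers, atypical antipsychotics and stimulants. Inclusion criterion 9 then asks for stability: "Subjects must be willing to refrain from treatment changes during the study protocol".

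**Data available.** The guardian reports current medications at the screening/baseline stage, and a study clinician will "review current medications and recommend any medication taper". New concomitant medications are listed weekly.

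**Allocation.** The only statement is "We will enroll 60 subjects to allow for the randomization of 30 subject into each treatment arm". No stratification factor is given.

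**Analysis.** The SAP (Statistical Methods) models mania and depression from "the study group, study week (continuous), and the study group-by-study week interaction", the interaction being the effect of interest. The two planned moderators are CBCL profiles. No covariate, subgroup or sensitivity analysis uses background medication.

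**Aim.** The hypothesis in Specific Aims is that "omega-3 fatty acids plus inositol combined intervention will result in improved outcomes relative to using NAC as monotherapy".

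**The concern.** By design, each arm will contain some children taking the study product alone and some taking it on top of another psychotropic. Treatment status at entry is plausibly related to the six-week course of mania and depression scores, although the documents give no figure for this. A baseline factor that predicts outcome, is already recorded and is absent from both allocation and model has two consequences in a trial of 60. Its share of the outcome variance stays in the error term, and any chance imbalance between arms passes into the group-by-week estimate uncorrected.

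There is also a gap in description. Neither document says that the estimated effect is an average over children with and without background treatment, and no table of background treatment by arm is planned. A reader of the result could not tell what mix of stand-alone and add-on use lies behind it.

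**Working it through.** **1. The plan's own figure.** 2 × 30 = 60 agrees with the stated enrolment. The documents give no power, effect size or SD, so nothing further can be reproduced. For scale, the standardised difference detectable with 80% power (two-sided 0.05, normal approximation) is (1.960 + 0.842) × √(2/30) = 0.72.

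**2. Assumed inputs, none in the documents.** Number K of the 60 children on a psychotropic: 15, 20 or 30. SD of P-YMRS change: 10 points. Difference in mean change between medicated and unmedicated children: 5 to 8 points, with 3 as a weaker case. The sums treat the outcome as a change score. The SAP plans a mixed-effects Poisson model, so they indicate scale only.

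**3. Chance imbalance.** With a fixed unstratified 30:30 split, the number of medicated children in one arm is hypergeometric (60, K, 30). A gap of 20 percentage points is 6 children.

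| K of 60 | P(gap of 20 points or more) |
|---|---|
| 15 | 0.072 |
| 20 | 0.170 |
| 30 | 0.196 |

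The value for K = 15 is low partly because an odd total cannot split with a gap of exactly 6. K = 14 gives 0.125 and K = 16 gives 0.143.

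**4. Shift in the contrast.** Shift = imbalance × difference: 0.20 × 5 = 1.0 point and 0.20 × 8 = 1.6 points. SE = 10 × √(2/30) = 2.58. The shift is 1.0/2.58 = 0.39 to 1.6/2.58 = 0.62 SE. With a 3-point difference it is 0.6/2.58 = 0.23 SE.

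**5. Precision.** The share of variance explained is R² = p(1 − p) × difference² / 100. Power is taken at a standardised difference of 0.72, with the SD multiplied by √(1 − R²). Unadjusted power is 0.80.

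| p | Difference | R² | Adjusted power |
|---|---|---|---|
| 0.25 | 3 | 0.017 | 0.80 |
| 0.25 | 5 | 0.047 | 0.81 |
| 0.25 | 8 | 0.120 | 0.84 |
| 0.50 | 3 | 0.022 | 0.81 |
| 0.50 | 5 | 0.062 | 0.82 |
| 0.50 | 8 | 0.160 | 0.86 |

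**6. Separating stand-alone from add-on use.** If half of each arm is medicated, there are 15 children per arm in each stratum. The detectable difference within a stratum is 2.802 × √(2/15) = 1.02 SD. For the medication-by-arm interaction it is 2.802 × √(4/15) = 1.45 SD. The trial can adjust for status but cannot reliably separate the two uses.

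**7. Order of events.** In the pandemic sequence, study product is dispensed before the week 99/0 tele-visit at which the clinician procedures are done. Medication review and taper advice are among those procedures. In an open-label trial the choice to continue or taper could then be made with the arm known. The documents do not say when randomisation occurs. A status settled after allocation may itself depend on the arm, so it is not a safe covariate.

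**The case against.** The strongest reply is that averaging over stable background treatment is a legitimate design. The same rule applies to both arms, and inclusion criterion 9 asks for no treatment changes. Status fixed before allocation is balanced in expectation, and the unadjusted standard error already allows for chance imbalance. The test is therefore valid, and the same argument could be made for age or diagnosis. The gain is small, and every size above rests on assumed inputs. All of this stands. It limits the point to precision and description, but does not remove the case for using a recorded and plausibly prognostic factor.

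A reader might infer more: that the hypothesis promises NAC without other drugs, so that the stated comparison is never estimated. The documents do not support this. In its sentence, monotherapy most naturally sets one supplement against a combination of two. Nothing in the protocol says that children take the study product without other psychotropics, and the taper paragraph plans openly for the opposite. The group-by-week term does compare the two-supplement combination with NAC. What remains is one ambiguous word.

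It is also fair to object that the SAP is written in the past tense and dated April 2025. If allocation is complete, stratification and new recording before allocation are no longer possible.

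**Conclusion.** The point holds as a modest one. The primary contrast is a valid, unadjusted average over children with and without background psychotropics. Leaving treatment status at entry out of the models gives up some precision and leaves chance imbalance uncorrected.

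Under the assumed inputs, a 20-point or larger imbalance has a chance of about 7% to 20%. It would move the contrast by about 0.4 to 0.6 SE. Adjustment raises power from 0.80 to between about 0.81 and 0.86. If status matters by only 3 points, the power gain is about 0.01 or less.

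Systematic bias is not shown. The pandemic sequence leaves open a route by which continue-or-taper choices could follow a known arm, but because the timing of randomisation is not stated, this remains a possibility and not a finding.

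**What to change.** - Add psychotropic status at consent (yes/no, fixed before allocation) and status-by-week to the P-YMRS and CDI models. The interaction is needed because the effect of interest is a slope, which a main effect alone does not adjust.
- If outcomes have already been analysed, present this as a sensitivity analysis labelled post hoc.
- Tabulate background medication by arm.
- State that the effect estimated is that of the study products given with or without continuing background treatment, and clarify the word monotherapy in Specific Aims.
- Do not adjust for medication status determined after allocation.
- Treat any estimate in children on no other psychotropic as descriptive only.
- If allocation is still open, stratify it by this status, and record both the status and the continue-or-taper intention before allocation.

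The cost is two extra parameters per model, one table and some wording. Current medications are already collected, and no extra children or visits are needed. The return is correspondingly small.
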